2.7.1.2.5 Maximum duration of dryness

The median maximum duration of dryness until Week 48/50 will be presented. The median, obtained from KM analysis will be presented along with the 2-sided 95% CI. KM plot will be provided.

The detailed Kaplan-Meier result will be presented including (week), number of patients under at risk (with fluids), number of patients without fluids (event), probability of dry retina (survival probability) and 95% CI.

Variable	Definition
Start date	Start date of dryness
Event	Dryness
End date of event	End date of dryness
Censoring (end date)	Earliest of: Presence of dryness until EOS Early discontinuation with presence of dryness
Duration of time	(End date – start date) +1 (Maximum duration will be used)

The above analysis will be done on the FAS and only on the study eye.

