2.3 Analysis sets

The Enrolled Set (ENR) includes all patients who signed an ICF and are assigned patient numbers.

The Safety Set (SAF) includes all patients who received at least one IVT injection of study treatment.

The Full Analysis Set (FAS) will be the same as the Safety Set in this study and will be used as primary population to analyze the efficacy endpoints.

Urgent Safety Measure Set (USM): If any subject needs Q4 treatment interval at any time point after initial loading phase then that subject qualify for USM.

The Per-Protocol Set (PPS) is a subset of patients in the FAS without PDs with impact. The list of PD criteria will be provided in edit checks specification (ECS) document.

Full Analysis Set Estimand (FAS-EST): The FAS-EST comprises all patients who are in FAS and did not discontinue treatment in the entire study due to COVID-19.

Per-Protocol Set Estimand (PPS-EST): The PPS-EST is a subset of patients of the FAS-EST without PDs with impact due to COVID-19.

When assessing the robustness of the overall efficacy conclusions, considerations will be given to the analysis based on the estimand using FAS-EST and PPS-EST. The expectation for comparing of both estimands is to have similar conclusions. Inconsistencies in the results will be examined and discussed in the CSR.

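### SAP 2.7.1.2.5: the event and risk-set labels for maximum duration of dryness contradict the section's own date and censoring rows, and the FAS label leaves never-dry eyes without a rule

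*SAP*

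**What the plan says.** SAP 2.7.1.2.5 defines the analysis in a table and a short text.

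- **Clock.** It starts at "Start date of dryness" and stops at "End date of dryness".
- **Event row.** The event is given as dryness.
- **Censoring.** Two cases are listed: "Presence of dryness until EOS" and "Early discontinuation with presence of dryness".
- **Spell used.** If an eye has several dry spells, "Maximum duration will be used".
- **Output.** The Kaplan-Meier listing is to show "number of patients under at risk (with fluids), number of patients without fluids (event), probability of dry retina (survival probability", with a 95% CI.
- **Population.** "The above analysis will be done on the FAS and only on the study eye". SAP 2.3 states: "The Full Analysis Set (FAS) will be the same as the Safety Set in this study". Membership does not depend on ever becoming dry, and neither do the exclusions in SAP Table 5-1.

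Three other places bear on this. The general definitions in SAP 2.1.1 make absence of fluid the dry-retina event and presence of fluid a reason for censoring; they also count sub-RPE fluid in the definition of dry retina. SAP 2.7.1.2.4 (time to dryness) uses the same at-risk and event labels as 2.7.1.2.5. The Kaplan-Meier code in SAP 5.4 treats the value 0 of the censoring variable as censored, but does not say which state is coded 0.

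**The concern.** A duration-of-dryness curve follows eyes that are dry and counts the moment fluid returns. An eye that already has fluid cannot be at risk of losing dryness. The Event row and the output text nevertheless place eyes with fluid in the risk set and call eyes without fluid the events. That layout belongs to time to dryness.

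Two things are at stake. First, the section gives the programmer two incompatible instructions for the event flag, and the medians they produce are not close. Second, a median presented as an FAS result would be read as applying to all treated eyes, when only eyes that dried at least once can contribute.

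**Working it through.** The documents give no figure for this analysis, so there is none to reproduce. The check sets the rows side by side and then illustrates the size.

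**1. Which analysis does each row describe?**

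| Element of SAP 2.7.1.2.5 | Time to dryness | Duration of dryness |
|---|---|---|
| Start = start of dryness | no | yes |
| End = end of dryness | no | yes |
| Censored if still dry at EOS | no | yes |
| Censored if discontinued while dry | no | yes |
| Survival probability = probability of dry retina | no | yes |
| Event = dryness | yes | no |
| At risk = eyes with fluid | yes | no |

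Five elements describe duration of dryness. Two describe time to dryness and match the labels in SAP 2.7.1.2.4.

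**2. Three hypothetical eyes**, using the section's duration formula (end − start + 1).

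- Eye A is dry from Week 8 and fluid returns at Week 28: (28 − 8) × 7 + 1 = 141 days. Under the date and censoring rows this is an event. Under SAP 2.1.1, presence of fluid makes it censored.
- Eye B is dry from Week 8 and still dry at Week 48: (48 − 8) × 7 + 1 = 281 days. Under the censoring rows it is censored. Under the Event row and SAP 2.1.1 it is an event.
- Eye C is never dry. It has no start date, so no duration can be computed. No rule excludes it or gives it zero.

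**3. How many eyes could resemble eye C?** The documents do not say. As a proxy only, Protocol 1.1 cites total fluid resolution in 60% to 72% of patients one year after a switch to another anti-VEGF agent. Applied to the planned 295:

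- 295 × 0.60 = 177 with a start date, leaving 295 − 177 = 118 without.
- 295 × 0.72 = 212 with a start date, leaving 295 − 212 = 83 without.

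The share dry at any visit could exceed the share dry at one year, so the number without a start date could be smaller.

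**4. Does the choice matter?** An illustrative simulation used 20,000 eyes per scenario. All inputs are assumptions: 60% or 72% ever dry; one exponential dry spell per ever-dry eye, with true median 8, 16 or 24 weeks; onset at Week 4, 8, 16 or 24 (probabilities 0.4, 0.3, 0.2, 0.1); assessment every 4 weeks; end at Week 48; no dropout. Kaplan-Meier medians in weeks:

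| Ever dry | True median | Return of fluid = event, ever-dry eyes | Same event, never-dry eyes = 0 | Flag reversed, ever-dry eyes |
|---|---|---|---|---|
| 60% | 8 | 12 | 4 | 44 |
| 60% | 16 | 16 | 8 | 40 |
| 60% | 24 | 28 | 8 | 40 |
| 72% | 8 | 8 | 8 | 44 |
| 72% | 16 | 20 | 12 | 40 |
| 72% | 24 | 28 | 16 | 40 |

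The first result column can sit one visit above the true median because durations are rounded up to the 4-week grid. In the last column, events can occur only when follow-up ends: 48 − 24 = 24, 48 − 16 = 32, 48 − 8 = 40 or 48 − 4 = 44 weeks. That median reflects follow-up after onset and hardly responds to how long eyes stay dry.

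**The case against.** The strongest reply is that the rows that generate the data are already right. Start, end and both censoring rules all describe duration of dryness, and the two labels that do not fit look carried over from time to dryness. A careful programmer would recover the intent, and SAP 1 assigns further programming detail to TFL shells and dataset specifications that are not available here. This stands in part. A reader might infer that the analysis will be run with events and risk set inverted, but the documents do not support that: it would require overriding the censoring rows. What remains is a contradiction that SAP 2.1.1 tilts the wrong way and the code does not resolve.

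A reader might also infer that never-dry eyes are hidden. They are not wholly hidden. SAP 2.7.1.2.3 reports fluid status on the FAS by visit and over the entire study, SAP 2.7.1.2.4 keeps never-dry eyes as censored, and 2.7.1.2.5 itself requires numbers at risk. The gap is a rule and a correct label for this one curve.

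A reader might take the result to overstate the durability endpoint. That endpoint is separate: Protocol Table 2-1 and SAP 2.7.1.3 define it by the last and maximal treatment intervals.

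Finally, using the longest spell may look like an error. The section's title declares the maximum as its quantity, so replacing it with the first spell would change the question asked.

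**Conclusion.** The concern holds as an internal contradiction plus a missing population rule. The Event row and the at-risk and event labels are the reverse of what the section's own dates and censoring require. As defined, the median can describe ever-dry eyes only, although the section places it on the FAS.

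The documents fix no size. Under the assumed simulation inputs, the flag and population choices move the median among 8 to 28, 40 to 44 and 4 to 16 weeks, so the choice is material to this result. The share of never-dry eyes is unknown; 83 to 118 of 295 rests on a proxy from other agents.

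The reach is limited. This is a descriptive analysis in the SAP, not among the endpoints in Protocol Table 2-1, with no hypothesis test, and the interim SAP marks it not applicable (2.8.1.2.5). The primary endpoint and the sample size are unaffected. It should still be corrected, because a stated analysis rule is wrong and the correction is cheap.

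**What to change.** In SAP 2.7.1.2.5:

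1. Set the event to return of IRF or SRF, and the risk set to eyes still dry. Correct the Event row and the output text together.
2. Keep the existing start, end and censoring rows, and state which state is coded 0 in the censoring variable.
3. State that the event and censoring definition for dry retina in SAP 2.1.1 does not apply to this analysis.
4. Use one definition of dry retina, neither IRF nor SRF, as in the protocol endpoint. SAP 2.1.1 adds sub-RPE fluid and should be aligned.
5. Label the population as FAS eyes that became dry at least once, and print the number and percentage of the FAS never dry beside the median.

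The longest spell may stay as the declared quantity. A first-spell curve is an optional supplement.

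The cost is SAP wording and a small programming change. No new data are needed.

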2.7.1.3 Durability

2.7.1.3.1 Last interval

The last treatment interval (defined by the investigator) before or at Week 48.

The distribution of the last interval, e.g., the proportion of last interval (Q8, Q12, and Q16) will be provided.

The above analysis will be done on the FAS and only on the study eye.

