- Similarly, inspection visits 14 weeks after the last injection can be performed at the Investigator's discretion when the injection interval is extended from 12 weeks to 16 weeks, respectively. If there is no disease activity in the study eye at the inspection visit as assessed by the Investigator, the study treatment will not be administered; the next visit and injection will take place 2 weeks later, i.e. 16 weeks after the previous study treatment. If disease activity is observed by the Investigator in the study eye at the inspection visit, the study treatment will be administered by the Investigator; the injection interval will be reduced to 12 weeks and the next injection visit will be 12 weeks after the inspection visit.
- The last potential study treatment may be administered at Week 44/46 according to the treatment schedule.
- A disease activity assessment will also be performed at the Week 48/EOS visit; however, no study treatment will be administered.

If a patient misses a disease activity assessment visits (Week 8 and the following), the patient should come to the visit as soon as possible. The investigator is recommended to consider the

patient to have met the disease activity criterion at the missed visit and the patient next treatment interval should be modified accordingly (e.g. shortened by 4 weeks).

If a patient misses Week 16, then the last visit values (Week 8 or Week 14) will be applied as the reference for disease activity assessments for the primary endpoint.

The different types of visits occurring through the study are summarized in [Table 6-3](#) with a description of when disease activity assessment and treatment will take place.

Table 6-3 Disease activity assessment and treatment occurrence according to visit type

Type	Study phase	Disease activity assessment	Treatment
Screening/Baseline (Day 1) Visit	Initiation Phase	Yes	Yes
Weeks 4 and 8 visits	Initiation Phase	Yes	Yes
Week 16 visit	Treat-to-Control Phase	Yes	Yes ^a
Treatment visits	Treat-to-Control Phase	Yes	Yes ^a
Inspection visits (optional)	Treat-to-Control Phase	Yes	Based on DA, as per Investigator's judgment
ETD visit and EOS visit (Week 48/50 ^b)	Follow up	Yes	No

^a Treatment according to Investigator's decision based on assessment of disease activity.

^b The EOS Visit will take place at least 4 weeks after the last injection, e.g. at Week 48 or at Week 50 for patients receiving his/her last injection at Week 46.

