12.5.3 Durability of brolucizumab 6 mg

Summary statistics of the time (in days) of the last interval with no disease activity before or at Week 48 will be provided. If there is disease activity, the last interval will be shortened by 4 weeks down to a minimum of 4 weeks. The distribution of the last interval is the proportion of subjects with no disease activity (Q4, Q8, and Q12) up to Week 48.

Summary statistics of time (in days) of the longest interval of treatment with no disease activity before or at Week 48 will be provided. The distribution of the maximal interval is the proportion of patients with no disease activity (Q8, Q12 and Q16) up to Week 48.

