1.2 Study objectives and endpoints

Table 2-1 Objectives and related endpoints

Objectives	Endpoints
Primary objective	Endpoint for primary objective
• To evaluate the effect of brolucizumab 6 mg on disease control	• Proportion of patients with no disease activity at Week 16
Secondary objectives	Endpoints for secondary objectives
• To evaluate the long term effects of brolucizumab 6 mg on disease control	• Proportion of patients with no disease activity at Week 48
• To evaluate the effect of brolucizumab 6 mg on anatomical parameters	• Change from Baseline in CSFT as assessed by OCT over time up to Week 48 • Absence of IRF, SRF, and sub-RPE fluid as assessed by OCT over time up to Week 48 • Proportion of patients with a dry retina (neither IRF nor SRF) up to Week 48
• To evaluate the durability of brolucizumab 6 mg	• Distribution of the last interval with no disease activity up to Week 48 • Distribution of the maximal intervals with no disease activity up to Week 48
• To evaluate functional outcomes	• Average change in BCVA from Baseline up to Week 48
• To assess the safety and tolerability of brolucizumab 6 mg	• Incidence of AEs (serious and non-serious) up to Week 48

AEs=adverse events, BCVA=best corrected visual acuity, [REDACTED] CSFT=central sub-field retinal thickness, [REDACTED] IRF=intraretinal fluid, OCT= optical coherence tomography, [REDACTED]
SRF= subretinal fluid.

2 Statistical methods

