Percent change from Baseline: The percent change from baseline will be calculated as below: $((\text{post-baseline value} - \text{Baseline value}) / \text{Baseline value}) * 100$.

Proportion: A proportion refers to the fraction of the total that possesses a certain attribute. In this study attribute is disease free activity.

Disease control: When patients have no disease activity after taking study treatment then patient will be consider as disease control.

On-treatment period: The on-treatment period lasts from the date of first administration of study treatment to 30 days after the date of the last actual administration of any study treatment.

Treatment duration: The maximum planned duration of treatment for each patient is 44 to 46 weeks in accordance with the designated treatment regimen. Discontinuation of study treatment for a patient occurs when study treatment is stopped earlier than the protocol planned duration and can be initiated by either the patient or the investigator.

Treatment discontinuation: When patients discontinue study treatment but continue in the study, the efficacy data will be used at the time the patient stopped study treatment.

Last interval: The last treatment interval (defined by the investigator) before Week 48.

Maximum interval: The longest interval of treatment reached by the patient over the study period.

Event for no disease activity: When patients will be with no disease status as per investigator decision after last dose in initiation phase then the patients will consider as event for no disease activity. If patients with active disease status or early discontinue then patients will be considered as censored for disease activity.

Dry retina: Absence of fluid (IRF/SRF/ sub-RPE) will be considered as dry retina.

Event for dry retina: When patients have absence of fluid then it will be considered as an event of dry retina. If patients have a presence of fluid before/at EOS or early discontinuation then will be censored.

[figure not shown]
Study eye and fellow eye: The investigator selects the eye with the worse BCVA at Screening as the study eye if both eyes are eligible as per the inclusion and exclusion criteria, unless the investigator deems as a study eye more appropriate to select the eye with better BCVA, based on medical reasons or local ethical requirements. If both eyes are eligible as per the inclusion and exclusion criteria, then it is recommended to select the right eye as the study eye.

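### The SAP's last-interval endpoint need not have elapsed or ended without disease activity, so it can credit 12- or 16-week durability that nobody observed

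*SAP*

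**What the plan says.** The SAP's objectives table (1.2) lists the endpoint as "Distribution of the last interval with no disease activity up to Week 48". The analysis text in SAP 2.7.1.3.1 drops the activity condition. It defines the quantity as "The last treatment interval (defined by the investigator) before or at Week 48" and says that "the proportion of last interval (Q8, Q12, and Q16) will be provided".

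The general definitions (SAP 2.1.1) give nearly the same wording, "Last interval: The last treatment interval (defined by the investigator) before Week 48", without the words that take in Week 48 itself. The next definition there, for the maximum interval, is worded differently: "The longest interval of treatment reached by the patient over the study period".

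Protocol 12.5.3 reads: "Summary statistics of the time (in days) of the last interval with no disease activity before or at Week 48 will be provided". It then takes 4 weeks off the last interval when there is disease activity, with a floor of 4 weeks, and lists the categories Q4, Q8 and Q12. Protocol 6.7.2.2 states: "A disease activity assessment will also be performed at the Week 48/EOS visit; however, no study treatment will be administered". SAP section 4 declares no change from the protocol's analyses.

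**The concern.** At each injection in the Treat-to-Control Phase the investigator sets the next interval. The one set at the final injection may run past the end of the study. If that value is tabulated, a patient injected at Week 44 and put on a 16-week interval appears under Q16 after 4 weeks of observation. Restoring the activity condition with the Week 48 reading does not cure this, because a quiet eye 4 weeks after an injection says little about weeks 5 to 16.

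Durability is a named secondary objective, and the Q12 and Q16 shares are the figures readers will take from it. The text also leaves open which interval is meant, so two programmers could produce different tables from the same data.

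**Working it through.** **Inputs**
- Intervals after Week 8 are 8, 12 or 16 weeks, lengthened or shortened by 4 weeks at a time. Q8 can be held from Week 16 and Q12 from Week 28 (protocol 6.7.2.2).
- An optional inspection visit at 10 weeks (extension from 8 to 12) or 14 weeks (12 to 16) can lead to an injection, followed by 8 or 12 weeks respectively (protocol 6.7.2.2).
- The last possible injection is at Week 44 or 46. EOS is Week 48, or Week 50 after a Week 46 injection (protocol section 3).

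**The plan's own figure.** The minimum follow-up after the last injection is 4 weeks: 48 − 44 = 4 and 50 − 46 = 4. It reproduces.

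**Enumeration.** I listed every nominal schedule from the Week 16 injection. Weeks observed = EOS week − final injection week. Fraction observed = weeks observed ÷ interval set at the final injection.

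| Final injection | EOS | Weeks observed | Q8 set | Q12 set | Q16 set |
|---|---|---|---|---|---|
| Week 36 | 48 | 12 | not final (next due Week 44) | 12/12 = 100% | 12/16 = 75% |
| Week 40 | 48 | 8 | 8/8 = 100% | 8/12 = 67% | 8/16 = 50% |
| Week 42 | 48 | 6 | 6/8 = 75% | 6/12 = 50% | not reachable |
| Week 44 | 48 | 4 | 4/8 = 50% | 4/12 = 33% | 4/16 = 25% |
| Week 46 | 50 | 4 | 4/8 = 50% | 4/12 = 33% | 4/16 = 25% |

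Allowing a direct step from 16 to 8 weeks changes nothing in the Q12 and Q16 columns.

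**Completed 16-week gaps.** A 16-week gap must follow a 12-week one and end by Week 46, so it must start by Week 30. The only such start is 16 + 12 = 28, which gives injections at Weeks 16, 28 and 44.

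**Schedules ending with each interval set**
- Q16: five schedules. Four (16-24-36, 16-28-40, 16-24-32-44 and 16-26-34-46) never contain a completed 16-week gap.
- Q12: 2 + 2 + 3 + 4 + 1 = 12 schedules, by final injection at Week 36, 40, 42, 44 and 46. The two ending at Week 36 are complete and the other ten are cut short.

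These are counts of possible schedules, not of patients.

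**Example.** Injections at Weeks 16, 24, 32 and 44, Q16 set at Week 44, no activity at Week 44 or 48. Counting the interval set at the last injection gives Q16. Counting the last completed interval (Week 32 to 44) gives Q12. The protocol's shortening rule does not alter the first result, because no activity was seen.

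**The case against.** The strongest reply is that the SAP never says it counts an unfinished interval. Every Treat-to-Control interval is chosen by the investigator, so the parenthesis may only describe how intervals arise, and the definition fits the interval that ended at the last injection equally well. Nothing states that an interval is recorded when no further study injection can follow. This stands: it is an open reading, not an established fact. The contrast with the maximum interval, which must be reached, favours the planned reading without settling it.

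Three stronger inferences are tempting, and the documents support none of them.
- **That the result always overstates durability.** A Q12 set at Week 36 and a Q8 set at Week 40 are fully observed. A patient injected at Weeks 16, 28 and 40 and cut to Q8 for activity at Week 40 is counted as Q8, despite an earlier quiet 12-week interval.
- **That the last interval is usually cut short.** No expected distribution of intervals is given.
- **That the protocol asks for a purely observed interval.** Its 4-week shortening rule adjusts the value, so it is partly a regimen measure. With the activity condition, that rule gives some protection, but SAP 2.7.1.3.1 carries neither.

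The endpoint is also descriptive, and other tables show the regimen at Week 48 (protocol 12.3) and interval changes (SAP 2.5.1). That limits the harm. It also means the durability endpoint should show more than the regimen.

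**Conclusion.** The concern holds as a gap in the definition. SAP 2.7.1.3.1 and 2.1.1 do not say which interval counts, do not require it to have elapsed, and omit the activity condition that belongs to the endpoint. If the interval set at the final injection is used, no final Q16 is ever complete (4 to 12 of 16 weeks seen), and a final Q12 is complete only from Week 36 (otherwise 4 to 8 of 12 weeks). The tendency is to overstate the Q12 and Q16 shares. By how much in patients cannot be said.

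The arithmetic assumes nominal visit weeks. It does not model the 7-day window or early treatment discontinuation, after which the patient is assessed 4 weeks after the last injection. The end-of-treatment weeks listed under the design figure run from 38 to 46 and omit Week 36. On that list alone the follow-up is 4 to 10 weeks (48 − 38 = 10), and no final Q12 or Q16 would be complete.

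**What to change.** In SAP 2.1.1 and 2.7.1.3.1:

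1. Derive the last interval from dates as the most recent completed one: either between two study injections, or from the last injection to EOS if the interval set has fully elapsed by then (for example, Week 40 to 48 on Q8).
2. Count it as free of disease activity only if none was recorded at its end.
3. If activity was recorded, do not go back to an earlier quiet interval. With injections at Weeks 16, 28 and 40, Q8 set at Week 40, and activity at Weeks 40 and 48, a look-back would credit Q12 to an eye active at its last two assessments. Either class the patient as not meeting the condition or apply the protocol 12.5.3 shortening rule, and state which.
4. Reconcile with protocol 12.5.3 on the activity condition, the shortening rule and the categories (Q4/Q8/Q12 against Q8/Q12/Q16), and use one wording for the Week 48 limit.
5. Report the interval set at the last injection in a separate table headed as planned.

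In SAP 2.7.1.3.2, state that the maximal interval must also be completed, in line with 2.1.1.

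The cost is SAP wording and one derivation from injection dates and visit-level activity readings already collected. No treatment rule changes. The Q12 and Q16 shares may come out less favourable.
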